5 STUDY POPULATION

Patients suffering from type 2 diabetes who meet the inclusion and exclusion criteria will be evaluated for participation in the study. To ensure participant safety in this early feasibility study, we aim to enroll individuals without significant cardiovascular conditions or other serious internal organ diseases.

A total of 20 participants will be enrolled at up to 5 study sites.

5.1 Inclusion Criteria

Participants are eligible to be included in the study only if all of the following criteria apply:

- 1. 22-65 years of age
- 2. Current diagnosis of T2D
- 3. History of T2D for at least 3 years and less than or equal to 10 years
- 4. HbA1C of 7.5-10.0%, inclusive
- 5. BMI 24-40 kg/m², inclusive
- 6. On two to three non-insulin glucose lowering mediations, with one at maximum tolerated dose and another at half-maximum dose at least, with no changes in medication for at least 12 weeks prior to baseline visit
- 7. History of failed attempt to reach glycemic goal by lifestyle modifications
- 8. Weight stability (defined as a < 5% change in body weight) for at least 12 weeks prior to the screening visit
- 9. Agree not to donate blood during participation in the study.
- 10. Able to comply with study requirements and understand and sign the Informed Consent Form
- 11. Women of childbearing potential must be using an acceptable method of contraception throughout the study
- 12. Willing and able to use CGM for the duration of the study and comply with study visits and study tasks as required per protocol.

5.2 Exclusion Criteria

Participants are excluded from the study if any of the following criteria apply:

- 1. Diagnosed with type 1 diabetes
- 2. History of diabetic ketoacidosis or hyperosmolar nonketotic coma
- 3. Probable insulin production failure, defined as overnight fasting C-peptide serum <1 ng/mL (333pmol/l).
- 4. Previous use of any types of insulin for >1 month (at any time, except for treatment of gestational diabetes) in last 2 years.
- 5. Current use of insulin
- 6. Hypoglycemia unawareness
- 7. History of ≥1 severe hypoglycemia episode (defined by needing for third-party assistance) in past 6 months from the screening visit
- 8. Known autoimmune disease, as evidenced by a positive anti-glutamic acid decarboxylase (GAD) test, including but not limited to celiac disease, or pre-existing symptoms of systemic lupus erythematosus, scleroderma or other autoimmune connective tissue disorder. (Participants with adequately controlled primary hypothyroidism may be included).
- 9. Previous GI surgery that has changed GI anatomy or could limit treatment of the duodenum, such as Billroth 2, Roux-en-Y gastric bypass, gastric band or other similar procedures or conditions.
- 10. Known history of a structural or functional disorder of the upper GI tract that may impede passage of the device through the upper GI tract or increase risk of tissue damage during an endoscopic procedure, including esophagitis, stricture/stenosis, varices, diverticula, or other disorder of the esophagus, stomach and duodenum.
- 11. Active H. pylori infection (Participants with active H. pylori may continue with the screening process if they are treated with an appropriate antibiotic regimen)
- 12. History of, or gastrointestinal symptoms suggestive of gastroparesis.
- 13. Acute gastrointestinal illness in the previous 7 days
- 14. Known history irritable bowel syndrome, radiation enteritis or other inflammatory bowel disease, such as Crohn's disease and Celiac disease
- 15. History of chronic or acute pancreatitis.
- 16. Known active hepatitis or active liver disease other than NASH/NAFLD.
- 17. Alcoholic liver disease, as indicated by a history of alcohol consumption and ANI >0
- 18. Current use of anticoagulation therapy (such as warfarin) that cannot be safely discontinued periprocedurally.
- 19. Current use of P2Y12 inhibitors (clopidogrel, prasugrel, ticagrelor) that cannot be discontinued for 7 days before the procedure.
- 20. Unable to discontinue non-steroidal anti-inflammatory drugs (NSAIDs) during treatment through 4 weeks following the procedure. Use of acetaminophen and low dose aspirin is allowed.
- 21. Use of systemic glucocorticoids (excluding topical or ophthalmic application or inhaled forms) for more than 10 consecutive days within 12 weeks prior to the baseline visit.
- 22. Use of drugs known to affect GI motility (e.g. Metoclopramide)

- 23. Use of weight loss medications such as Phentermine, Meridia, Xenical, or over-the-counter weight loss medications (prescription medication)
- 24. Currently taking, or unable to stop taking dietary supplements or herbal agents, including vitamin C or multivitamins contained vitamin C at >500 mg per day, multivitamins containing biotin (vitamin B7), and supplements for hair, skin, and nail growth. Multivitamins not containing biotin are permitted.
- 25. Persistent anemia, defined as hemoglobin <10 g/dL.
- 26. Known history of hemoglobinopathy.
- 27. Known history of blood donation or transfusion within 3 months prior to the Screening Visit.
- 28. Known history of cardiac arrythmia
- 29. Significant cardiovascular disease, including known history of valvular disease, or myocardial infarction, heart failure, transient ischemic attack, or stroke within 6 months prior to the Screening Visit
- 30. Estimated glomerular filtration rate (eGFR) \leq 60 ml/min/1.73m² (estimated by MDRD)
- 31. Known immunocompromised status, including but not limited to individuals who have undergone organ transplantation, chemotherapy, or radiotherapy within the past 12 months, who have clinically significant leukopenia, who are positive for the human immunodeficiency virus (HIV) or whose immune status makes the participant a poor candidate for clinical trial participation in the opinion of the investigator.
- 32. History of secondary hypothyroidism or inadequately controlled primary hypothyroidism (TSH value outside the normal range at screening)
- 33. With any implanted electronic devices that can't be turned off during the procedure, or duodenal or biliary stents.
- 34. Not a candidate for upper GI endoscopy or general anesthesia.
- 35. Active illicit substance abuse or alcoholism (> 2 drinks/day regularly).
- 36. Active malignancy within the last 5 years (excluding non-melanoma skin cancers)
- 37. Women breast feeding
- 38. Participating in another ongoing clinical trial of an investigational drug or device.
- 39. Any other mental or physical condition which, in the opinion of the study investigator, makes the participant a poor candidate for clinical trial participation.
- 40. Critically ill or has a life expectancy < 3 years

Additional exclusion criteria to be confirmed during the screening process:

- 41. HbA1c < 7.5% or > 10% at baseline visit
- 42. Any severe hypoglycemic event since the screening visit
- 43. CGM readings of <54 mg/dl in more than 1% of time since the screening visit with at least 5 days of CGM data.
- 44. CGM readings of >360 mg/dl in more than 1% of time since the screening visit with at least 5 days of CGM data.
- 45. Mean of 3 separate blood pressure measurements >180 mmHg (systolic) or >100 mmHg (diastolic)

- 46. Women of child-bearing potential with a positive urine pregnancy test at baseline visit
- 47. Grade III or greater esophagitis on endoscopy
- 48. Abnormalities of the GI tract preventing endoscopic access to the duodenum
- 49. Anatomic abnormalities in the duodenum that would preclude the completion of the treatment procedure, including tortuous anatomy
- 50. Endoscopic observation of upper gastrointestinal abnormality such as ulcers, duodenal polyps in the area to be treated, varices, strictures, congenital or intestinal telangiectasia
- 51. Any other anatomical or endoscopic abnormalities/characteristics that, in the opinion of the investigator, would preclude safe use of the investigational device or procedure.

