5.3 Point of Enrollment

The point of enrollment occurs when a participant has provided written informed consent and the Endogenex catheter insertion has been attempted during the index procedure.

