7.13.1 Screening Visit – Visit 1 (within 84 days from the Index Procedure)

To limit in-person visit, the screening visit may be performed remotely. Screening BMI eligibility will be based on self-reported height and weight. Potentially eligible participants will be scheduled for laboratory tests at the study laboratory. The following procedures/assessments will be performed during this visit:

- Informed consent prior to the conduct of any study-related procedures
- Inclusion and exclusion criteria
- Demographics
- Medical history including diseases, disorders and medications
- Diabetes history including diabetes medications
- Laboratory tests:
 - o Hematology (CBC with differentials)
 - Metabolic panel (liver and renal function)
 - o Fasting serum C-peptide, FPG, HbA1C

- GAD antibodies
- o TSH
- H. Pylori (breath or stool test)
- Pregnancy test for females capable of becoming pregnant
- Registration on screening log

Once all data including testing results related to the screening have been obtained, the investigator will review the participant's eligibility for the study. If deemed eligible, participant will be scheduled for the baseline visit.

Eligible participant must meet all the inclusion criteria and none of the exclusion criteria with one exception. If a participant has met all other criteria except that s/he has been on stable glucose-lowering medication(s) for less than 12 weeks at the time of screening visit, the participant can be scheduled for baseline visit such that s/he will be on stable medication for 12 weeks at the time of baseline visit.

It is recognized that COVID-19 restrictions may cause delays in scheduling the index procedure, resulting in the screening visit being out of window. In case the screening visit is out of the visit window, the investigator will reassess the participant's eligibility by evaluating any changes in the participant's medical history and medications. The investigator may decide to repeat certain screening tests based on his/her medical judgement. If the investigator determines that the participant remains eligible for participating in the study, the participant may proceed to Baseline visit. Investigator's assessment and any repeated test results will be documented on eCRFs.

7.13.2 Baseline Visit – Visit 2 (within 21 days prior to the Index Procedure)

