This visit will be performed onsite. The following evaluations/procedures are to be performed. Participant's study eligibility will be reconfirmed at this visit.

- Physical examination
- Anthropometric measurements including height, weight and waist circumference
- Vital signs
- Adverse event (changes in medical history)
- Concomitant medications
- 12-lead EKG
- Laboratory tests:
 - o Hematology (CBC with differentials)
 - Metabolic panel
 - o Glycemic parameters (HbA1C, MMTT, HOMA-IR)
 - Fasting lipid panel
 - o Lipase, Amylase
 - o Serum iron, ferritin, transferrin, saturation, serum folate, Vitamin D, Vitamin B12
 - o International normalized ratio (INR) for participants on Warfarin (may be performed on Day 0)
- H. Pylori breath or stool test
- Pregnancy test for females capable of becoming pregnant
- Assessment for eligibility
- Preparation with gastroenterologist for procedure, medication management per Section 6.
- Diabetes education, including instruction on CGM use
- Treating physician review of diabetes history and titration of glucose-lowing medications per Section 6.2
- Review CGM data
- Lifestyle counselling

If the participant is no longer eligible for the study due to a change in the participant's condition, such as pregnancy, abnormal blood test values, HbA1C outside of the protocol range, or weight change resulting in a BMI outside of the protocol range, the participant will be excluded from the study and documented as a screen failure.

The screening and baseline visit may be combined if the screening visit falls within the baseline visit window. In this case, data collected during the combined visit will serve as both screen and baseline data.

It is recognized that new COVID-19 restrictions may cause delays in scheduling the index procedure, resulting in the baseline visit out of window. In case the baseline visit is out of visit window, investigator will reassess participant's eligibility by evaluating any changes in participant's medical history and medications, Investigator's assessment will be documented on eCRF. The following tests will be repeated for safety considerations or to serve as baseline data:

- Laboratory tests:
 - Hematology (CBC with differentials)
 - o Glycemic parameters (FPG, HbA1C, insulin, HOMA-IR)
- Pregnancy test for females capable of becoming pregnant (may be performed on Day 0)
- Anthropometric measurements including weight and waist circumference (may be collected on Day
 0)

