7.13.3 Index Procedure Visit – Visit 3 (Day 0)

See Section 6.1 for details of the index procedure and post procedure instructions.

The following assessments/procedures will be performed.

- Handout participant study ID card
- Vital signs prior to discharge
- Concomitant medications
- Assessment of AEs
- Diabetes review and medication titration by treating physician

Participants will be instructed on transitional diet, the importance of hydration, use of CGM for the duration of the study, monitoring and preventing hypoglycemic events.

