Serum Iron, ferritin, transferrin, saturation, serum folate, Vitamin D, Vitamin B12		Х									Х						X	Х	
CBC with differential	X	X		X		X		X			X			X			X	X	
Serum Glutamic acid decarboxylase antibody (Anti-GAD)	X																		
Thyroid-stimulating hormone (TSH)	X							$X^{[3]}$			$X^{[3]}$			$X^{[3]}$			$X^{[3]}$		
H. Pylori test	X	X																	
Pregnancy test [4]	X	X																	
International Normalized Ratio (INR) [7)		X																	
EKG		X																	
ENDOSCOPIES																			
DMR procedure			X																
Endoscopic follow up						X					X ^[5]								
SAFETY																			
Hypoglycaemic episodes	X	X	X	X	X	X	X	X	X	X	X	X	X	X	X	X	X	X	X
CGM		X	X	X	X	X	X	X	X	X	X	X	X	X	X	X	Х	X	X
Adverse events	X	X	X	X	X	X	X	X	X	X	X	X	X	X	X	X	X	X	X

^[1] Screening and baseline visits may be combined if screening visits or tests falls within baseline visit window.

^[2] Metabolic panel includes albumin, total protein, ALP, ALT, AST, bilirubin, BUN, creatinine, BUN/creatinine ratio, eGFR.

^[3] For participants on oral thyroid replacement therapy only.

^[4] For women with child-bearing potential.

^[5] Required if there were positive findings in the treated area at the 4-week endoscopy.

^[6] Only when MMTT is not performed.

^[7] INR is required prior to procedure only if participant is on Warfarin.

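### The last pregnancy test the protocol requires can be up to 21 days old at the index procedure; a urine test on Day 0 would close the gap cheaply

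*Protocol*

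**What the plan says.** Three parts of the protocol set the timing of pregnancy testing.

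- **Eligibility.** Criterion 46 in Section 5.2 excludes "Women of child-bearing potential with a positive urine pregnancy test at baseline visit". The copy in the Protocol Summary is the same. Neither mentions Day 0.
- **Visits.** Sections 7.13.1 and 7.13.2 each list a pregnancy test, and the row in the Schedule of Activities (Appendix 2) carries two marks, which match those visits. The heading of Section 7.13.2 places baseline "within 21 days prior to the Index Procedure", and Appendix 2 gives the window as Day -21 to Day -1.
- **Day 0.** Section 7.13.3 opens its list with "The following assessments/procedures will be performed". It then names the ID card, vital signs, concomitant medications, adverse events and the diabetes review. Pregnancy testing is absent.

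Day 0 testing appears in one place only. If COVID-19 delays push the baseline visit out of window, Section 7.13.2 requires certain tests to be repeated, among them "Pregnancy test for females capable of becoming pregnant (may be performed on Day 0". For an in-window baseline, the INR may be done on Day 0, but the pregnancy test carries no such note.

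The other stated control is inclusion criterion 11 in Section 5.1: "Women of childbearing potential must be using an acceptable method of contraception throughout the study".

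**The concern.** The protocol treats pregnancy as a change that can arise between visits. It tests at screening, tests again at baseline, and names pregnancy in Section 7.13.2 as a reason to exclude at baseline. The same reasoning covers the interval from baseline to the procedure, which can last three weeks, yet no test is required at its end.

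What is at stake is exposure. Section 2.4 states that no clinical data exist with this device. The procedure is done under general anesthesia or deep sedation, and Section 6.1 allows fluoroscopy when needed. Section 9.1.1 counts fetal distress, fetal death and congenital abnormality among the serious outcomes, so the protocol itself regards fetal harm as serious. A participant could comply in full, be pregnant on Day 0, and still be treated.

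**Working it through.** The plan states no figure for the age of the last test, so there is nothing to reproduce. The check is arithmetic on the visit windows.

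**Inputs**
- Screening window: Day -84 to Day -5 (Appendix 2).
- Baseline window: Day -21 to Day -1 (Appendix 2; heading of Section 7.13.2).
- Required tests: screening 1, baseline 1, index procedure 0 (Sections 7.13.1 to 7.13.3; Appendix 2).
- Follow-up: 48 weeks (Section 4.1).

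**Step 1. Age of the last required test, separate visits.** Age = 0 minus the test day.
- Latest baseline: 0 - (-1) = 1 day.
- Earliest baseline: 0 - (-21) = 21 days.

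The range is 1 to 21 days.

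**Step 2. Combined visit.** Section 7.13.2 says "The screening and baseline visit may be combined if the screening visit falls within the baseline visit window". The two windows overlap from the later start, max(-84, -21) = -21, to the earlier end, min(-5, -1) = -5. The test is then 5 to 21 days old. The maximum is again 21.

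**Step 3. Baseline out of window.** The test must be repeated. Day 0 is allowed for the repeat but not required.

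**Step 4. With a required Day 0 test.** The age of the last test is 0 days in every case, a reduction of 1 to 21 days for in-window participants.

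**Step 5. What a positive Day 0 result would mean.** Under Section 5.3 a participant is enrolled only once consent is given and "the Endogenex catheter insertion has been attempted during the index procedure". A test done before that point leaves a woman with a positive result unenrolled. She is then a screen failure under Section 5.4, with no device exposure.

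**Step 6. How much of the pregnancy-related loss to follow-up this could prevent.** Pregnancy ends remaining follow-up at any time (Section 8.2). Follow-up is 48 x 7 = 336 days and the longest gap before Day 0 is 21 days. If the risk is assumed constant over both periods, the gap is at most 21 / (21 + 336) = 21 / 357 = 5.9% of the time at risk. The other 94% or so falls after Day 0, where this fix has no effect.

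**A different window in the SAP.** The visit table in SAP Section 8.6 shows baseline as Day -28 to Day -1, which would make the maximum 28 days. The protocol governs conduct, so 21 days is the figure used here.

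**The case against.** The strongest reply is that the controls are already layered. Contraception is required throughout, pregnancy is tested at screening and baseline, and the test is repeated if baseline falls out of window. Section 6.1 leaves preparation for anesthesia and endoscopy to institutional practice, which may include a same-day test. Exclusions 34 and 39 let the investigator decline an unsuitable candidate. The residual gap needs a pregnancy to arise, or to become detectable, within a few weeks despite contraception. This argument stands as to likelihood: the case would be uncommon, and the documents give no number of women of childbearing potential from which to estimate it. It does not close the gap, because none of these provisions requires a test after baseline, and with up to 5 sites local practice may differ.

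A second reply is that little remains to act on. The SAP Introduction tabulates 3 + 7 + 10 = 20 patients, the full planned number, and early exits are not replaced (Section 8.2). This also stands, and it limits where the change can apply.

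A reader might infer two stronger points that the documents do not support.

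- **That combining visits makes matters worse.** One test then serves both visits, but what counts is the age of the latest negative result, and its maximum stays at 21 days. An earlier negative from screening adds little once a later one exists.
- **That the gap threatens the trial's data.** Loss of one participant out of 20 is the same fraction for any dropout and does not measure this problem. A participant who becomes pregnant stays in the ITT population (Section 12.3), and her available data are used (Section 12.4.1). Step 6 shows that most pregnancy-related exits would arise after Day 0 anyway.

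**Conclusion.** The point holds as a cheap patient-safety improvement. For in-window participants, the last required pregnancy test is 1 to 21 days old at the index procedure, and a Day 0 test would bring that to 0. This rests on the protocol's visit windows, its Day 0 list and the wording of criterion 46. It needs no assumption about event rates.

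It is not an internal error, and nothing in the documents is breached by a 21-day window. No expected number of exposed pregnancies is claimed. Nor is anything claimed about the consent form, the Instructions for Use or the Investigator's Brochure, which are not among the documents reviewed. The case rests on avoiding exposure alone, not on retention or precision.

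**What to change.** 1. In Section 7.13.3, add a urine pregnancy test for women of childbearing potential, done before anesthesia and endoscopic screening.
2. In Appendix 2, mark the pregnancy-test row in the index-procedure column.
3. In both copies of criterion 46 (Protocol Summary and Section 5.2), change the timing to *at baseline visit or on Day 0*.
4. State that a positive Day 0 result is a screen failure under Section 5.4.

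The cost is one bullet, one table mark, a few words in two places, one short statement, and one urine test per woman of childbearing potential. Section 7.13.2 already accepts Day 0 as workable for the repeat pregnancy test. A urine test can miss a very early pregnancy, so the contraception requirement must stay. As enrollment appears complete, the change applies to any remaining procedures or to a later version of the protocol.

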5.3 Point of Enrollment

The point of enrollment occurs when a participant has provided written informed consent and the Endogenex catheter insertion has been attempted during the index procedure.

5.4 Screen Failures

Screen failures are defined as participants who consented to participate in the clinical study and started the screening tests specified by the protocol but are not subsequently enrolled in the study. Screen failure information including demography, screen failure details, eligibility criteria, and any serious adverse event (SAE) will be documented on eCRFs.

Individuals who do not meet the criteria for participation in this study (screen failure) may be rescreened. Data from all screen and re-screen visits will be captured on eCRFs.

Individuals who failed at endoscopic screening will be followed for four weeks for safety.

6 STUDY INTERVENTION AND CONCOMITANT THERAPY

6.1 Study Intervention (Index Procedure)

The study intervention is the duodenal mucosal regeneration (DMR) procedure using the Endogenex Device.

The DMR procedure is performed under general anesthesia or deep sedation. Participants will be prepared for anesthesia and upper endoscopy according to institution's standard practice.

At the beginning of the procedure, participants will undergo endoscopic assessment to confirm endoscopic eligibility. Participants who meet the endoscopic eligibility will undergo the DMR procedure following the procedure steps described in the Instruction for Use (IFU). In brief, the catheter is inserted trans-orally into the participant's duodenum under endoscopic visualization. Fluoroscopy maybe used to guide the catheter insertion when needed. The catheter's flex circuit section is positioned approximately 2cm distal to the Papilla of Vater. The flex circuit board is deployed to achieve contact between the duodenal wall and the electrodes on the circuit board. Energy delivery is initiated by pressing the "Start" button on the generator. Upon completion of energy delivery, the circuit board is retracted into the housing in a compressed configuration and moved distally to the next treatment zone. The procedure is repeated until the treatment length is up to 14cm approximately. Upon completion of the treatment, the catheter is removed, and a final endoscopic inspection is performed.

Participant will be recovered from anesthesia and discharged according to local institution's discharge criteria and procedures. An overnight stay is not required but permitted per investigator's clinical judgement.

Before the participant is discharged, s/he is to be provided with a study information card. This card provides the phone number and name of the person to contact in case s/he needs medical attention related to the therapy. Additionally, the participant can provide this card to an emergency room doctor, allowing them to contact the Primary Investigator and obtain information about the study. A sample of the card is provided in **Appendix 3**.

The participant will be placed on a clear liquid diet for 24 hours, followed by a full liquid diet for 3 days, pureed food for 3 days, soft food for one week, and then return to normal food as tolerated.

Antiemetic (such as Ondansetron) and antispasmodics (such as hyoscyamine) may be provided on standby following the DMR procedure, and the participants should be educated on their use.

Participants who are excluded during endoscopic screening will be considered a screening failure and be followed for four weeks for safety.

A participant is considered enrolled in the study when the participant has given written informed consent and the Endogenex catheter insertion is attempted.

